## 16.3. Auditing

During the running of the study, Solvay Dental 360™ may appoint Quality Assurance (QA) personnel to provide audit of the administration and conduct of the study, both at the investigation site and at Solvay Dental 360™.

The relevant Regulatory Authority also has the right to conduct an audit of the study, that the study was, in fact, performed at stated investigation sites and that the data reported to the authority in support of a marketing application accurately reflects the data in the records of the Principal Investigator. The authority also inspects such studies to verify that the studies were conducted in accordance with Government regulations relating to the IRB and informed consent. It is the joint responsibility of the Sponsor and the Principal Investigator to ensure that the study has been conducted in line with all government regulations.

In the event that the regulatory authority desires to inspect this study, the Principal Investigator will permit authorized inspectors to inspect all facilities and records relating to the study and aid the Inspector to perform the audit in a timely fashion.

#### **16.4. Modifications to protocol**

Except in emergency situations, prior approval by the Sponsor is required for changes in or deviations from this Protocol. This provision does not apply to those changes made to reduce discomfort or overt risks to the subject. In the event of an emergency situation, the Principal Investigator must institute any and all medical procedures he/she deems to be medically sound. All such events and procedures must be documented in the subjects electronic Case Report Form and reported to the sponsor or designee within 3 days.

#### **16.5. Procedure for reporting any protocol deviations**

The investigator should avoid deviating from the protocol. All deviations related to the study inclusion or exclusion criteria, conduct of the investigation, patient management, or patient assessment are to be documented on the eCRF provided for that purpose. Notification to the IRB should be documented and maintained in the clinical investigator file (as required).

4. Software

All tables, listings and figures will be produced using SAS Version 9.4 (SAS Institute, Cary, NC.) or a later version of SAS. All output will be in Microsoft Word or RTF format.

5. Definitions

CoCr	- Cobalt Chrome
CRF	- Case Report Form
OHIP	- Oral Health Impact Profile
OHRQoL	- Oral Health-related Quality of Life
RPD	- Removable Partial Denture
SOC	- Standard of Care

6. Trial Objectives

The primary objective is to evaluate the change in patient Oral Health-related Quality of Life (OHRQoL) while wearing a cobalt chrome (CoCr) removable partial denture (RPD) compared to after wearing the Solvay Dental 360TM polymer Removable Partial Denture (RPD) for 8 weeks.

The secondary objectives are:

1. To investigate the difference in health of the abutment teeth following the use of the polymer Removable Partial Denture (RPD) as compared to the Cobalt Chrome (CoCr) Removable Partial Denture (RPD) as assessed by the plaque score and gingival bleeding index.

2. To investigate the difference in whole plaque score following the use of the polymer Removable Partial Denture (RPD) as compared to the cobalt chrome (CoCr) Removable Partial Denture (RPD).
3. To investigate the health of the mucosal bearing areas of the polymer Removable Partial Denture (RPD) as compared to the cobalt chrome (CoCr) Removable Partial Denture (RPD).
4. To investigate the framework hygiene (disclosing), probing depths, and abutment tooth mobility.
5. To investigate the professional (operator) based outcomes for the fit, fusion, occlusion and aesthetics.
6. To investigate the patient assessment of the comfort, aesthetics and chewing ability after the polymer Removable Partial Denture (RPD) and then Cobalt Chrome (CoCr) Removable Partial Denture (RPD).
7. To determine the denture preference of each patient.

7. Trial Hypotheses

The primary endpoint analysis will be performed on all subjects with an overall score reported on the OHIP questionnaire for both the Cobalt Chrome and Polymer Frame. The primary endpoint in this study is the OHIP overall score after wearing the Cobalt Chrome frame versus the OHIP overall score after wearing the Polymer frame. The hypothesis can be written as follows:

$$H_0: OS_{\text{diff}} > \Delta \text{ versus}$$

$$H_A: OS_{\text{diff}} \leq \Delta,$$

where

- OS_{diff} is the overall score for the cobalt chrome frame subtracted from the overall score for the polymer frame
- Δ is the performance goal

No formal hypothesis testing will be done for the secondary endpoints.

8. Trial Success Criteria

Success of the primary endpoints will be based on a significance level of $\alpha = 0.05$. That is, if the hypothesis test results in a p-value that is less than 0.05, the study will be considered a success.

9. Trial Design

This is a multi-center, cohort study conducted in the United States and United Kingdom that will enroll approximately 40 subjects to assess Oral Health Related Quality of Life (OHRQoL) in patients receiving the study polymer Removable Partial Denture (RPD) as compared to their baseline Cobalt Chrome (CoCr) Removable Partial Denture (RPD) Oral Health Related Quality of Life (OHRQoL).

Subjects who are current wearers of a Cobalt Chrome (CoCr) Removable Partial Denture (RPD) will complete an Oral Health Related Quality of Life (OHRQoL) instrument, the Oral Health Impact Profile (OHIP) questionnaire, at baseline and again after wearing their prescribed polymer Removable Partial Denture (RPD) for 8 weeks.

9.1 Randomization

Randomization will not be used in this study as it is a single-arm cohort study.

9.2 Blinding

Blinding will not be used in this study.

10. Sample Size Considerations

Power calculations of the non-inferiority of the overall score on the OHIP questionnaire for subjects wearing a polymer frame versus the overall score on the OHIP questionnaire for subjects wearing a cobalt chrome denture were based on a non-inferiority test for one mean where higher means are worse and $\alpha=0.05$.

In a previous study (S. Shaghaghian, 2014), the average overall score on the OHIP questionnaire for subjects wearing a cobalt chrome denture was 13.8 (standard deviation = 10.1). Based on the anticipated improved performance of the polymer frame, 36 subjects provides approximately 80% power to detect a difference of -3 (standard deviation = 11) between the 2 overall scores with a non-inferiority margin of 1.5. The total number of subjects enrolled will be 40, given the anticipated attrition rate of 10%.

11. Data Structure and Handling

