When evaluating or comparing treatment options, variables such as survival rate and longevity of the prostheses, and frequency of complications have been regarded as the most important outcomes for clinicians; however, the social and psychological impacts of treatment, cost effectiveness, benefit, and utility are more important factors from the patient's perspective (Furuyama, 2011).

Patient's satisfaction or dissatisfaction with their partial dentures is an important part of the removable partial denture (RPD) treatment. Patients adapt to partial dentures individually, depending on their prior experience, expectations, emotional and general health status, as well as on the status of the oral cavity. For some patients, satisfaction with partial dentures relates primarily to comfort and ability to masticate, while aesthetics and retention are more important for others (Dubravka, 2000).

In addition, the condition, number, and alignment of the abutment teeth; the gingival, periodontal, and mucosal tissue health; the type of the construction and denture support; and the material and denture base shape are also common reasons for patient dissatisfaction. Other factors dependent on the patient may be the quality of the denture-supporting area and oral mucosa, influence of the surrounding muscles on the denture flanges, viscosity of saliva, patient's age and ability to get used to the denture, state of the abutments, condition of the other teeth in the mouth, relation between the horizontal and vertical dimensions of occlusion, hygiene habits, diet, presence of chronic diseases, position of the patient's teeth in the mouth, and quality of the removable appliance. (Reference: Treatment Outcomes with Removable Partial Dentures: A Comparison

Between Patient and Prosthodontist Assessments). Therefore, a thorough initial oral exam is a critical step in the preparation for the insertion of the Removable Partial Denture (RPD).

There is a need to assess the impact of polymer removable partial dentures (RPDs) on overall patient oral health and quality of life. Based on previous studies and literature, Removable Partial Denture (RPD) alternatives, such as polymer Removable Partial Dentures (RPDs), should be considered and assessed, with Oral Health Related Quality of Life (OHRQoL) validated instruments and patient satisfaction surveys.

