### **3. Objectives**

#### **3.1. Hypothesis**

Patient Oral Health-related Quality of Life (OHRQoL) after wearing the Solvay Dental 360™ polymer Removable Partial Denture (RPD) is non-inferior to patient Oral Health-related Quality of Life (OHRQoL) after wearing a cobalt chrome (CoCr) Removable Partial Denture (RPD).

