## 12.2. Sample Size Determination

In a previous study (S. Shaghaghian, 2014), the average overall score on the OHIP questionnaire for subjects wearing a cobalt chrome denture was 13.8 (standard deviation = 10.1). Based on the anticipated improved performance of the polymer frame, 36 subjects with an alpha level of 0.05 provides approximately 80% power to detect a difference of -3 (standard deviation = 11) between the 2 overall scores with a non-inferiority margin of 1.5. The total number of subjects enrolled will be 40, given the anticipated attrition rate of 10%.

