12.1 General Considerations

Continuous measures will be summarized with sample size, mean, median, standard deviation, minimum and maximum; categorical measures will be presented with the counts and percentages of subjects in each category.

The date of enrollment will be considered study day 1.

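### Is the sample size inadequate because its 80% power rests on an assumed 3-point gain for the polymer denture?

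*SAP*

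**What the plan says.** Protocol section 3.1 sets the hypothesis: quality of life with the polymer denture "is non-inferior to patient Oral Health-related Quality of Life (OHRQoL) after wearing a cobalt chrome (CoCr) Removable Partial Denture (RPD"). Protocol 12.1.1 and 12.1.3 and SAP 12.5.1.2 test the mean change in OHIP-14 score (polymer minus CoCr, higher is worse) against 1.5 points, with a one-sample t-test.

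SAP section 10 describes the calculation as a "non-inferiority test for one mean where higher means are worse" and gives its result: "Based on the anticipated improved performance of the polymer frame, 36 subjects provides approximately 80% power to detect a difference of -3". Protocol 12.2 likewise states that "36 subjects with an alpha level of 0.05 provides approximately 80% power" at a true difference of -3 with SD 11. Both documents give the same reason, an anticipated better performance of the polymer frame, and both allow for 10% attrition, hence 40 enrolled.

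The only outside figures cited are for CoCr wearers: "the average overall score on the OHIP questionnaire for subjects wearing a cobalt chrome denture was 13.8 (standard deviation = 10.1").

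On reading the result, SAP section 8 says "if the hypothesis test results in a p-value that is less than 0.05, the study will be considered a success". On summaries, SAP 12.1 says "Continuous measures will be summarized with sample size, mean, median, standard deviation, minimum and maximum".

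**The concern.** A non-inferiority trial is often expected to have good power when the two treatments are truly the same. Here the 80% applies only if the polymer denture is 3 points better. Nothing cited supports that figure: the earlier study has no polymer data, and the protocol's own rationale (section 2) says "There is a need to assess the impact of polymer removable partial dentures (RPDs) on overall patient oral health and quality of life". The SD of 11 for the within-patient change is also unsourced, since 10.1 is the SD of a single score.

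If the dentures are equivalent, the hypothesis is true, yet the trial would probably miss its goal. The plan gives no power at any other difference, names no confidence interval among its summaries, and does not say how a p-value of 0.05 or more will be read. A sponsor could therefore run the study with too optimistic a view of its chance of success.

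**Working it through.** **Inputs.** From protocol 12.2 and SAP 10: n = 36 evaluable, SD of change 11, true difference d = -3, margin 1.5, alpha 0.05, attrition 10%. Neither document states the sidedness in words. I take it as one-sided because the hypothesis is directional and because only that reading reproduces the stated power.

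**The plan's own figure.** The standard error is 11/√36 = 1.833. By the normal formula, power = Φ((1.5 − d)/SE − 1.645) = Φ(4.5/1.833 − 1.645) = Φ(0.81) = 79.1%. The exact noncentral t (35 df) gives 77.7%. At one-sided 0.025 the figures are 69.0% and 66.5%, so that reading does not fit. Attrition: 36/0.9 = 40, as stated. If all 40 are evaluable, exact power is 81.5%. The statement of approximately 80% is sound.

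**Observed mean needed to pass** (if the observed SD is 11):
- n = 36: 1.5 − 1.690 × 1.833 = 1.5 − 3.10 = −1.60
- n = 40: 1.5 − 1.685 × 1.739 = 1.5 − 2.93 = −1.43

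**Power at other true differences** (exact t, one-sided 0.05, SD 11):

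| True difference | n = 36 | n = 40 |
|---|---|---|
| 0 | 20.0% | 21.3% |
| −1 | 37.9% | 40.8% |
| −1.5 | 48.4% | 52.0% |
| −2 | 59.0% | 63.0% |
| −3 | 77.7% | 81.5% |

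At a true difference of +1.5, the margin itself, the pass rate is 5.0% at either size.

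**Dependence on the SD.** If the SD is 10.1 at both visits (an assumption), the SD of change is 10.1 × √(2(1 − r)), where r is the within-patient correlation. The planned 11 corresponds to r = 1 − 121/(2 × 10.1²) = 0.41. At n = 36:

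| r | SD of change | Mean needed to pass | Power at 0 | Power at −3 |
|---|---|---|---|---|
| 0.2 | 12.8 | −2.10 | 17% | 67% |
| 0.6 | 9.0 | −1.04 | 25% | 90% |
| 0.7 | 7.8 | −0.70 | 30% | 96% |
| 0.8 | 6.4 | −0.30 | 40% | 99% |
| 0.9 | 4.5 | +0.23 | 62% | over 99% |

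Power at equality reaches 80% only at a correlation of about 0.94 (SD about 3.5).

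**Size needed for 80% power** (exact t, SD 11): 39 evaluable at −3, 85 at −1.5 and 334 at 0. The last means 334/0.9 = 371.1, so 372 enrolled, or 372/40 = 9.3 times the planned number.

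**What an added interval would do.** The upper one-sided 95% limit is mean + t × SD/√n. It lies below 1.5 exactly when the one-sided p-value against 1.5 is below 0.05. The mean, SD and sample size are already among the planned summaries, so the interval can be computed from what will be reported.

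**The case for a change.** The strongest case for a change is that, once a non-inferiority trial is sized on superiority, the assumed gain carries the whole design and should be justified. Half the assumed gain brings power at n = 36 down to 48.4%. A label, a source, a short power table, a stated one-sided level and a 90% interval would cost almost nothing and would tell readers what the 80% depends on.

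Much of this stands. The arithmetic is right, the sources are missing, and over the whole range of correlations from 0.2 to 0.9 power at equality stays below 80%. Three things weaken it as a demand for change. First, the plan already says that the gain is anticipated, so a reader is not misled about its status; what is missing is its basis. The rationale in protocol section 2 is a general reason for doing the study and does not contradict expecting a benefit. Second, the headline figures of 20% and −1.60 hold only if the SD of change is 11. The t-test will use the observed SD, and a tighter one would help. Third, neither document treats a p-value of 0.05 or more as showing inferiority, so the feared misreading comes from a hypothetical reader and not from the plan.

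A middle course, such as 85 evaluable patients for 80% power at −1.5, would more than double the study and still rest on an assumed benefit.

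**Conclusion.** No change is called for. Sizing a non-inferiority test on an expected benefit is a legitimate choice, openly made, and the stated power follows from its inputs. The price is a high chance of missing the goal if the benefit is small: about 80% at true equality and about 52% at a 1.5-point gain, with 36 evaluable, SD 11 and one-sided 0.05. That risk falls on the sponsor's chance of success and not on the validity of a positive result, since the error rate at the margin remains 5%.

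The one remedy that would cure low power at equality, about 334 evaluable patients, is out of proportion to a post-market study of 40 at no more than 3 sites. The other possible additions (sources for −3 and SD 11, power at smaller differences, the one-sided level in words, an interval for the mean change) are details that a competent analyst can supply in the report. They leave the decision rule, the error rate and the result as they are.

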11.1 Data Handling and Transfer

Data management will be undertaken by NAMSA. NAMSA Biostatistics will be provided access to download SAS datasets or will be provided them upon request.

Programming of analysis datasets, tables, figures and listings will be conducted during the data management phase of the study. Tables, figures, and listings may be reviewed prior to final data lock for data review. Any data values requiring investigation or correction will be identified, and protocol deviations will be reviewed. The final run of outputs will take place after the data is deemed final.

11.2 Missing Data

Endpoint data may be missing because patients have died, refused follow-up, or have withdrawn from the study. The missing data does not bias the results as long as the data is missing at random. The primary analysis will be done on all patients who have an overall score from the baseline and 8 week OHIP questionnaire.

All efforts will be made to obtain information regarding subject's overall score on the OHIP questionnaire. The sponsor will report the reason for censoring for all subjects with missing endpoint data.

11.3 Visit Windows

There are 8 scheduled visits throughout the duration of the study. There are no windows specific to timing of each visit. The 8 visits are defined as follows:

Pre-Treatment Evaluations:

Visit 1: Eligibility, consent, initial impressions taken)

Treatment Evaluations:

Visit 2: Patient Identification number assigned, 2nd impression taken

Visit 3: Standard of Care (SOC) visit for prescribing Removable Partial Dentures (RPDs). Assess cast.

Visit 4: Trial Insertion.

Visit 5: Denture Fit.

Visit 6: Recall 1 week

Visit 7: Recall 4 week

Visit 8: Recall 8 week

11.4 Pooling of Data Across Trial Sites

Data from all study sites will be pooled. Poolability analyses will be performed on the primary endpoint to assess whether results are poolable across the participating centers.

A linear regression model with change in the overall score of the OHIP questionnaire as the dependent variable will be reported using a categorical variable for site. If there is evidence that the data is not poolable across centers, examination of the data will be performed to determine the underlying cause(s).

12. Statistical Analyses

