### 12.1.5. Poolability Analyses

Poolability analyses will be performed on the primary endpoint to assess whether results are poolable across the participating centers.

A linear regression model with change in the summary score of the Oral Health related Quality of Life Questionnaire as the dependent variable will be reported using a categorical variable for site. If there is evidence that the data is not poolable across centers, examination of the data will be performed to determine the underlying cause(s).

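### The poolability regression has site as its only named term; adding the Visit 2 OHIP score beside it, not instead of it, would sharpen the plan's one check of consistency between sites

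*SAP*

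**What the plan says.** Protocol 12.1.5 and SAP 11.4 describe the same model. In the SAP, "A linear regression model with change in the overall score of the OHIP questionnaire as the dependent variable will be reported"; in the protocol, the change score is taken "as the dependent variable will be reported using a categorical variable for site". Neither section names a second term, and baseline OHIP enters no model in either document.

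The baseline score is available. OHIP is completed at Visit 2 and Visit 8 (Protocol 7.3; SAP 12.5.1.3), and the primary analysis is limited to subjects with both scores (SAP 11.2 and 12.2).

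SAP 11.4 also states, without condition, that the sites' data will be pooled. If the sites appear to differ, the only consequence is a search for causes. Neither document says what result would count as evidence against pooling. SAP 12.8 plans no subset analyses, so this regression is the only planned look at consistency between sites.

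**The concern.** A change score usually depends on its own starting value. A subject with a high (poor) OHIP score at Visit 2 has more room to fall, and part of a high score is chance that will not recur. A model that omits the starting value leaves that variation in the residual, where it obscures real differences between sites. With about 12 analysed subjects per site, the check has little precision to spare.

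A second effect is possible. If the US and UK sites recruit patients with different starting scores, the site term may pick up that difference as well as any difference in how the polymer frame performs. A reader of the site-only result could not tell the two apart.

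What is at stake is how the pooled result is interpreted across sites. The success decision is not at stake.

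**Working it through.** **1. The plan's own figure.** SAP 10 uses a "non-inferiority test for one mean where higher means are worse", sized "to detect a difference of -3 (standard deviation = 11) between the 2 overall scores" and "with a non-inferiority margin of 1.5". At one-sided 0.05 and 80% power:

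n = [11 × (1.645 + 0.842) / (1.5 − (−3))]² = (11 × 2.487 / 4.5)² ≈ 37.

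Power at 36 = Φ(4.5 / (11/√36) − 1.645) = Φ(2.455 − 1.645) = 79.1%. Attrition: 36 / 0.9 = 40. The stated 36 subjects, about 80% power and 40 enrolled therefore reproduce (normal approximation). No power is stated for the poolability check.

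**2. What baseline could explain.** The documents give a CoCr score SD of 10.1, from a previous study, and a change SD of 11 (Protocol 12.2, SAP 10). They give no follow-up SD and no correlation. *Assumption:* follow-up SD = 10.1, with a range of 8 to 12.

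- ρ = (10.1² + 10.1² − 11²) / (2 × 10.1 × 10.1) = 83.02 / 204.02 = 0.407
- Slope of change on baseline = ρ × (10.1/10.1) − 1 = −0.593
- R² = (−0.593 × 10.1 / 11)² = 0.297
- Residual SD = 11 × √(1 − 0.297) = 9.23; variance ratio 11² / 9.23² = 1.42

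**3. Power to see a real site difference.** *Assumptions:* three sites (the maximum in Protocol 4.2), 36 / 3 = 12 analysed subjects each, test at 0.05. Power comes from the noncentral F with λ = 12 × Σ(site deviation from the mean)² / residual variance. Degrees of freedom are 2 and 33 without baseline, 2 and 32 with it.

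- One site off by 10 points: Σ = 3.33² + 3.33² + 6.67² = 66.7, so 12 × 66.7 = 800. Without baseline, λ = 800/121 = 6.61 and power is 59%. With it, λ = 800/85.1 = 9.40 and power is 75%.
- Sites spread evenly over 10 points: Σ = 5² + 0 + 5² = 50, so 12 × 50 = 600. Without baseline, λ = 600/121 = 4.96 and power is 46%. With it, λ = 600/85.1 = 7.05 and power is 61%.

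| Follow-up SD (assumed) | ρ | Slope | Residual SD | Power with baseline, one site off by 10 (59% without) |
|---|---|---|---|---|
| 8 | 0.279 | −0.78 | 7.7 | 89% |
| 10.1 | 0.407 | −0.59 | 9.2 | 75% |
| 12 | 0.516 | −0.39 | 10.3 | 65% |

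For one site off by 8 points, power goes from 40% to 54%. For 5 points it goes from 18% to 24%, which is uninformative either way. Unequal sites of 16, 10 and 10 with an even 10-point spread give 48% and 61% by simulation, so the gain does not need equal sites.

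**4. Sites that differ only in starting score.** Let one site start 5 or 10 points higher, with follow-up SD 10.1. Two patterns are possible.

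- *Between-site differences regress as within-site ones do.* Mean change at the high site differs by 0.593 × 5 = 3.0 or 0.593 × 10 = 5.9 points. Then Σ = (2/3) × difference², so λ = 12 × (2/3) × 2.965² / 121 = 0.58 or 12 × (2/3) × 5.93² / 121 = 2.33. The site-only model flags about 9% or 24%; the adjusted model stays near 5%.
- *Between-site differences are stable.* The site is higher by the same amount at both visits, so mean change is equal everywhere. In simulation the site-only model stays near 5%, and the adjusted model flags about 10% or 27%.

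**The case against.** The strongest reply is that no decision rests on this regression. The data are pooled whatever it shows, SAP 8 bases success on the primary p-value alone, and the planned search for causes could look at baseline OHIP, which is already collected. This stands, and it keeps the severity low. It does not remove the point: with no criterion stated for non-poolability, bringing in baseline only after an unwelcome result would be a choice made after seeing the data.

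A reader might infer something stronger: that the planned model will make sites look non-poolable merely because they recruit worse or better starters, and should be replaced by the adjusted one. The documents do not support that. They say nothing about how starting scores vary between sites or whether such differences persist. Under the stable pattern the planned model is the correct one and the replacement would create the false signal. Even under the regressing pattern, mean change truly differs between sites, and mean change is what the primary t-test pools; whether that flag is false depends on the question asked.

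Nor do the plan's SDs alone imply a slope of −0.59. That needs a follow-up SD that the plan does not give. The power gain also depends on large deviations: 10 points is close to one baseline SD, on a mean of 13.8.

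**Conclusion.** The point holds as a modest loss of sensitivity in the plan's only site-consistency check. Under the stated assumptions, leaving baseline OHIP out costs about 15 percentage points of power for a 10-point site difference, whether one site stands apart or the sites are spread evenly. For a single outlying site the gain from adding it runs from about 6 points (follow-up SD 12) to about 30 points (follow-up SD 8).

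This rests on three assumptions that the documents do not settle: the follow-up SD, three sites of 12, and a 0.05 threshold. The power gain does not depend on sites differing at baseline. The false-flag argument does, and its direction depends on an unknown between-site pattern, so it supports showing both models and does not favour one over the other. The primary test, the sample size and the success rule are unaffected.

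**What to change.** In Protocol 12.1.5 and SAP 11.4, keep the regression of OHIP change on site and pre-specify beside it the same regression with the Visit 2 OHIP score as a covariate. Next to the pooled result, report for each site the mean Visit 2 score, the unadjusted mean change and the baseline-adjusted mean change, both changes with 95% confidence intervals. If the two models disagree, the site baseline means show whether a difference in starting scores could be the reason. Leave the primary one-sample t-test as it is.

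The cost is a sentence or two in each document, one covariate in the program and one degree of freedom in the second model. No new data are needed. The downside is two sets of site results that may differ and must be read together.
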